#### **4.1 Randomisation and Blinding**

N.A.

#### **4.2 Contraception and Pregnancy Testing**

Patients who are pregnant will be excluded from this study

#### **4.3 Study Visits and Procedures**

##### **4.3.1 Screening Visits and Procedures**

Using Ushio's prototype, narrow-band 222 nm UV light will be irradiated onto selected pressure sores area for 90 seconds, 2 times per week over 2 week duration after the wound is cleaned and dry.

No additional hospital visits will be required.

Regular wound cleaning / debridement and dressings of the pressure sore will be performed

##### **4.3.2 Study Visits and Procedures**

Using Ushio's prototype, narrow-band 222 nm UV light will be irradiated onto selected pressure sores area for 90 seconds, 2 times per week over 2 week duration after the wound is cleaned and dry.

No additional hospital visits will be required.

Regular wound cleaning / debridement and dressings of the pressure sore will be performed

##### **4.3.3 Final Study Visit:**

Final study visit will be the last day of the 2 week long treatment process

##### **4.3.4 Post Study Follow up and Procedures**

N.A.

## **4.4 Discontinuation/Withdrawal**

### **4.4.1 Discontinuation Criteria**

N.A.

### **4.4.2 Discontinuation Visit and Procedures**

N.A.

## **5 TRIAL MATERIALS**

N.A.

### **5.1 Trial Product (s)**

A prototype UV photo-disinfection device developed by Ushio. It consists of a 222nm light emitting device which is made up of a lamp house and a main body.

### **5.2 Storage and Drug Accountability**

The product will be stored in a room temperature, dry storage area. The product will be tested the day before designated therapy with the trial subjects.

## **6 TREATMENT**

### **6.1 Rationale for Selection of Dose**

N.A.

### **6.2 Study Drug Formulations**

Using Ushio's prototype, narrow-band 222 nm UV light will be irradiated onto selected pressure sores area for 90 seconds, 2 times per week over 2 week duration after the wound is cleaned and 2dry

### **6.3 Study Drug Administration**

Using Ushio's prototype, narrow-band 222 nm UV light will be irradiated onto selected pressure sores area for 90 seconds, 2 times per week over 2 week duration after the wound is cleaned and dry

### **6.4 Specific Restrictions / Requirements**

N.A.

### **6.5 Blinding**

N.A.

## **6.6 Concomitant therapy**

Regular wound debridement and dressing changes will be performed as per regular treatment for pressure sores.

## **7 SAFETY MEASUREMENTS**

### **7.1 Definitions**

An adverse event (AE) is any untoward medical occurrence in a patient or clinical investigation subject administered a pharmaceutical product and which does not necessarily have a causal relationship with this treatment.

A serious adverse event (SAE) or reaction is any untoward medical occurrence that at any dose:

- results in death
- is life-threatening
- requires inpatient hospitalisation or prolongation of existing hospitalisation
- results in persistent or significant disability/incapacity or
- is a congenital anomaly/birth defect
- is a medical event that may jeopardize the patient and may require medical or surgical intervention to prevent one of the outcomes listed above.

### **7.2 Collecting, Recording and Reporting of Adverse Events and Serious Adverse Events to DSRB**

Reporting of adverse events involves the PI submitting to the approving DSRB the completed SAE Reporting Form within the stipulated timeframe. PI is responsible for informing the institution representative (local SAE resulting in death), sponsor or regulatory bodies as required and appropriate.

### **7.3 Collecting, Recording and Reporting of Serious Adverse Events (SAEs) to the Health Science Authority (HSA)**

All SAEs that are unexpected and related to the study drug will be reported to HSA. All SAEs will be reported to HSA according to the HSA Guidance for Industry “Safety Reporting Requirements for Clinical Drug Trials.”

The investigator is responsible for informing HSA no later than 15 calendar days after first knowledge that the case qualifies for expedited reporting. Follow-up information will be actively sought and submitted as it becomes available. For fatal or life-threatening cases, HSA will be notified as soon as possible but no later than 7 calendar days after first knowledge that a case qualifies, followed by a complete report within 8 additional calendar days.

## **8 DATA ANALYSIS**

### **8.1 Data Quality Assurance**

Pictures of the wound before and after UV treatment will be taken and healing rate will be measure using Pictzar program. Healing rate will be estimated by scaling the size, the colors, the edge form and the elasticity by using a camera until the sores heal up to 50% to the full recovering.

Pictures and samples will be taken by the same person to prevent any variance in sampling techniques

The investigators and the collaborators in the study team will be responsible for the safety of the data.

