### **4 STUDY DESIGN**

20 patients with presence of pressure sore estimate at 2 cm X 2 cm or bigger will be recruited in NUH for a period of 2 years. Using Ushio's prototype, narrow-band 222 nm UV light will be irradiated onto selected pressure sore area for 90 seconds, 2 times per week over 2 weeks duration after the wound is cleaned and dry. A plastic sheet with a hole of 2 cm X 2 cm will be used to guide the UV Light positioning on the pressure sore and to ensure that irradiation is shielded and will be blocked to only target at the selected pressure sore area. The UV light will be held at 1cm above the pressure sore. Wound culture and sensitivity before and immediately after each UV treatment will be done to determine if there is any decrease in bacteria count. Result can be used to determine the presence of wound infections prior to/after the UV treatment. Secondary to that, pictures of the selected pressure sore area before and after UV treatment will be taken and healing rate will be measure using Pictzar program. Healing rate will be estimated by scaling the size, the color, the edge form and the elasticity by using a color camera until the sores heal up to 50% to the full recovering to see if there is any decrease in wound size. After the trial, researchers will suggest improvements to the device from clinical perspective which will lead to mass production types. Successful result will be followed by a

larger scale clinical test at NUHS with joint application to Japan (AMED) and Singapore government grants, and joint marketing strategy to Asia

A more detailed description of the process of sample collection is attached in Appendix 1.

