### Procedure to obtain wound swab samples

1	Consent obtained from patient
2	Wound is exposed
3	Bedside wound debridement is performed 

- Eschar is excised

- Slough removed

4	Irrigation of the wound with 0.9% Normal saline to be performed
5	A photo of the wound using the designated study camera to be taken
6	A Tegaderm with the wound dimensions is fashioned and applied over the wound, exposing the wound bed but covering the wound edges
7	A swab of the wound bed is taken. *
8	One time use pre-made 2x2 headframe is put over the UV light device
9	UV light therapy is commenced over the wound bed 1 cm from the wound bed for 90sec at 6mJ/second for a total of 540 mJ 

- The device is to be held directly above the wound bed at right angles

10	A swab of the wound bed is taken immediately after UV light therapy *
11	The Tegaderm is removed
12	A photo of the wound using the designated study camera to be taken
13	The wound is dressed with Allevyn dressing

\*Wound swab samples to be taken with sterile wound swab tip.

The samples will be stored in a sterile dry tube and send to the Microbiology Lab at NUH

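### One unmasked person takes every before and after swab and photograph and no masked reading is specified, so bias in collection or photograph scaling could not be separated from a UV effect

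*Protocol*

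**What the plan says.** Section 4 describes one group of 20 patients, treated "2 times per week over 2 weeks duration after the wound is cleaned and dry". There is no comparison group.

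- **Bacterial outcome (Section 4):** "Wound culture and sensitivity before and immediately after each UV treatment will be done to determine if there is any decrease in bacteria count".
- **Healing outcome (Sections 4 and 8.1):** photographs are measured with the Pictzar program, and size, colour, edge form and elasticity are scaled, "to see if there is any decrease in wound size". The person who reads the photographs is not named.
- **Masking:** Section 4.1, "Randomisation and Blinding", and Section 6.5 both read N.A.
- **Safeguard (Section 8.1):** "Pictures and samples will be taken by the same person to prevent any variance in sampling techniques".
- **Sampling (Appendix 1):** a photograph and a swab come before irradiation. Then "A swab of the wound bed is taken immediately after UV light therapy", and a second photograph follows. Swabs go to the hospital's microbiology laboratory. The appendix does not say how tubes are labelled or whether the laboratory knows the time point.
- **Access to data:** pictures are kept on the principal investigator's laptop and are open to the study team (Section 8.2). Culture times and results are recorded and reviewed monthly by the principal investigator (Sections 11 and 12.2). The study team is also the attending team (Section 12.1).

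**The concern.** Section 8.1 treats the use of one operator as protection for the measurements. It does protect against one thing, which is differences in technique between operators. It does not protect against that operator swabbing or photographing differently before and after irradiation. If such a habit exists, using one person carries it into every patient, and averaging over patients does not remove it.

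The person holding the swab or camera cannot be masked. The person who later traces and scales a digital image can be, and so can a laboratory that receives a tube. The protocol specifies neither. Colour, edge and elasticity are matters of judgement, and tracing a wound margin is partly so.

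The usual partial remedy is a control group measured in the same way, and this study has none. Any consistent shift in collection or reading would be added directly to the estimated effect. Section 4 intends a successful result to lead to a larger study, so a spurious decrease would have consequences.

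**Working it through.** The protocol gives no sample-size, alpha or power figure (Sections 9.1 and 9.2 are N.A.), so there is no stated number to reproduce. The check has two parts.

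**1. How much material is exposed**

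Inputs from Section 4 and Appendix 1: 20 patients, 2 sessions a week for 2 weeks, one swab and one photograph before and after each session.

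- Sessions per patient: 2 × 2 = 4.
- Before/after pairs: 20 × 4 = 80.
- Swabs: 80 × 2 = 160. Photographs: also 160.

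**2. What a consistent shift would do (illustration only)**

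Assumptions that are not in the protocol: no true effect; one change per patient, normally distributed; a systematic shift of *b* standard deviations of that change towards a decrease; a two-sided 5% paired t test on 20 patients.

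Formulas: non-centrality = *b* × √20, with √20 = 4.472; degrees of freedom = 19; critical value = 2.093. P(positive test) is the probability that a non-central t falls outside ±2.093. P(mean decrease) = Φ(*b* × √20).

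| Shift *b* (SD) | Non-centrality | P(positive test) | P(mean decrease) |
|---|---|---|---|
| 0 | 0 | 5% | 50% |
| 0.2 | 0.894 | 13.6% | 81% |
| 0.3 | 1.342 | 24.7% | 91% |
| 0.5 | 2.236 | 56.5% | 99% |

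With a shift present, nearly all positive tests point towards a decrease: 13.3%, 24.6% and 56.4% in the three biased rows.

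A sign test points the same way and needs no SD. At least 15 of 20 patients must show a decrease for a two-sided p below 0.05 (p = 0.041). The chance of reaching 15 is 2% if a decrease is 50% likely by chance, 13% if bias makes it 60% likely, and 42% at 70%.

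**Where the shift could enter**

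- *Photograph scaling:* most exposed, because it is judged and no masked reader is described.
- *Swab collection:* exposed, because the operator knows the time point.
- *Laboratory culture:* less exposed, because a separate laboratory does it. Its masking is unknown.

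**The case against.** Four objections deserve weight.

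**The protocol does not say that anything is read with the time point known.** A reader might infer from Section 8.1 that swabs and photographs are read unmasked and that one person handles them throughout. The documents do not support that. The sentence is about who takes them. Swabs are processed by the hospital laboratory, and the photograph reader is not named. Unmasked photograph reading is a fair inference, since no masking is described and the team has open access. For swabs it is not documented. This objection stands, and the point is limited accordingly.

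**N.A. may refer only to treatment allocation.** Section 4.1 pairs blinding with randomisation, and Section 6.5 sits under treatment. In a single-arm study that is a natural reading, so N.A. should not be taken as a decision against masked assessment. But no other section supplies masked assessment, and Section 8.1, where it would belong, relies on the single operator. Nor can this be left to a statistical analysis plan, because tube labels and image files are handled before any analysis.

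**The size is assumed.** The shifts and the t test are not in the protocol. Section 4 states a purpose and defines no success rule, so the mean-decrease column tests a rule the protocol never adopts. This stands: the figures show sensitivity and do not estimate the bias.

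**Masked reading cures only part of the problem.** It leaves differential swabbing untouched. It also leaves a cause that needs no observer bias: the first swab may remove organisms from the same wound bed shortly before the second. This stands too, and it limits what the fix can claim.

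**Conclusion.** The point holds in a limited form. One person who knows the time point takes all the swabs and photographs, and no masked reading is specified. Healing is scored partly by judgement, and there is no control. A systematic before/after difference in collection or photograph scaling could therefore not be separated from a UV effect, and relying on a single operator does not address it.

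The documents do not show that such bias will occur, that it will favour UV, or how large it would be. The rise from 5% to between 13.6% and 56.5% positive tests depends on assumed shifts of 0.2 to 0.5 SD and an assumed test. Nor do the documents support the stronger claim that observer bias affects both outcomes equally. Photographs are the weaker outcome here, and the laboratory cultures are better placed.

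The change should be made before recruitment because it is cheap and cannot be made once the readings exist. It does not by itself make the before/after comparison interpretable.

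**What to change.** Keep the single operator for sampling. In Sections 4.1 and 6.5, replace N.A. with a statement that treatment is not masked but outcome reading is. Give the procedure in Section 8.1:

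1. **Photographs.** Store them under random file names with date and session removed. An existing team member other than the operator traces and scales them in Pictzar in random order. The key is opened only after all areas are locked. Appendix 1 takes the first photograph before the film is applied and the second after it is removed, so the film does not reveal the time point.
2. **Swabs.** Tubes and laboratory requests carry a random code with no before/after or session label. An existing team member who does not read photographs holds the key and may release individual culture results needed for care.
3. **Consistency.** Reconcile the key rule with the use of culture results to detect infection (Section 4), team access to pictures (Section 8.2) and the principal investigator's monthly review, which covers culture times and results (Sections 11 and 12.2).
4. **Stated limit.** Say that this removes reading bias only. It does not remove bias in swab collection, removal of organisms by the first swab, or the lack of a control.

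Cost: one code list, 160 tube labels, renaming 160 image files, and a division of roles within the existing team. No patient procedure is added. The downside is that a culture result needed for care must be traced through the key.

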### **8.2 Data Entry and Storage**

The pictures and data will be kept for the duration of the study in the PI password protected Laptop. The study team members will have access to the pictures or data if they need it.

## **9 SAMPLE SIZE AND STATISTICAL METHODS**

### **9.1 Determination of Sample Size**

N.A

### **9.2 Statistical and Analytical Plans**

N.A

## **10 DIRECT ACCESS TO SOURCE DATA/DOCUMENTS**

Study members will be given direct access to data should they need it

## **11 QUALITY CONTROL AND QUALITY ASSURANCE**

The investigators and the collaborators in the study team will be responsible for the safety and accuracy of the data.

The electronically stored data will include minimal necessary information mainly wound sites, sites where culture is taken, time where culture is taken, result of culture test, some demographic data and details of treatment implemented.

It will be reviewed by the PI on a monthly basis. Any significant findings will be recorded as well.

## **12 ETHICAL CONSIDERATIONS**

This study will be conducted in accordance with the ethical principles that have their origin in the Declaration of Helsinki and that are consistent with the Singapore Good Clinical Practice and the applicable regulatory requirements.

The principle investigator is responsible for informing the DSRB and HSA of any amendments to the protocol or other study-related documents, as per local requirement.

### **12.1 Informed Consent**

After the team has discussed the treatment plan to the potential research participant, they will be given adequate time to consider whether they want to participate in our research study. Consent process will only take place after potential research participant consider that option in either the Outpatient Clinic or Inpatient Ward setting.

The study team who are also the attending team will be taking the consent

Potential research participant will be given adequate time to consider whether they want to participate in our research study before any consent is taken from them

### **12.2 Confidentiality of Data and Patient Records**

The electronically stored data will include minimal necessary information mainly wound sites, sites where culture is taken, time where culture is taken, result of culture test, some demographic data and details of treatment implemented. It will be reviewed by the PI on a monthly basis. No patient identifiers will be taken during the study

## **13 PUBLICATIONS**

N.A.

## **14 RETENTION OF TRIAL DOCUMENTS**

Pictures and data will be deleted after the data has been published

## **15 FUNDING and INSURANCE**

National Clinical Trial Insurance will be responsible for payment and compensation of injury or illness arising from participation of subjects in the study

The study is funded by the GCC grant call.

# **List of Attachments**

**Appendix 1      Wound Sampling procedure**

## Appendix 1

### Procedure to obtain wound swab samples

1	Consent obtained from patient
2	Wound is exposed
3	Bedside wound debridement is performed 

- Eschar is excised

- Slough removed

4	Irrigation of the wound with 0.9% Normal saline to be performed
5	A photo of the wound using the designated study camera to be taken
6	A Tegaderm with the wound dimensions is fashioned and applied over the wound, exposing the wound bed but covering the wound edges
7	A swab of the wound bed is taken. *
8	One time use pre-made 2x2 headframe is put over the UV light device
9	UV light therapy is commenced over the wound bed 1 cm from the wound bed for 90sec at 6mJ/second for a total of 540 mJ 

- The device is to be held directly above the wound bed at right angles

10	A swab of the wound bed is taken immediately after UV light therapy *
11	The Tegaderm is removed
12	A photo of the wound using the designated study camera to be taken
13	The wound is dressed with Allevyn dressing

\*Wound swab samples to be taken with sterile wound swab tip.

The samples will be stored in a sterile dry tube and send to the Microbiology Lab at NUH
